2.3.2 KNOWN POTENTIAL BENEFITS

Potential immediate benefits include reduction of pain due to musculoskeletal injuries and global improvements in psychological health. Potential long-term benefits include improved functionality and work productivity, reduced opioid use, and improves in global physical health.

2.3.3 ASSESSMENT OF POTENTIAL RISKS AND BENEFITS

The TENS unit is an FDA-approved over-the-counter consumer-grade device and is contraindicative in women who are pregnant. Pregnant women were excluded from the study to minimize risk from the TENS unit. Virtual reality hardware and software has advanced significantly this decade and sophisticated motion tracking eliminates helps to minimize discomfort among participants. Modern studies utilizing VR have found general satisfaction with devices among participants. Still, individuals with neurological disorders or hypersensitivity to lights were excluded to minimize risk from VR exposure. Participation in the study may alleviate pain among individuals who have previously relied on opioids, subsequently decreasing both opioid-induced side effects and providing pain relief. Sustained pain relief may allow individuals to return to work faster, improve physical mobility, and enhance biopsychosocial health. We believe the short- and long-term anticipated benefits outweigh minimal short-term risks.

To minimize risk of breaches in confidentiality associated with the access and recording of protected health information, study staff will be assigned unique passwords and usernames to access secure servers. Additionally, identifiable information for participants will be obfuscated using unique ID numbers and a linking list will be held in a secure location.

3 OBJECTIVES AND ENDPOINTS

OBJECTIVES	ENDPOINTS	JUSTIFICATION FOR ENDPOINTS
Primary		
The primary objective of this study is to develop and validate a multi- modal digital pain reduction kit for improving physical function over time.	The primary endpoint in this study is a clinically significant change in self- reported physical function over time among individuals in the intervention arm compared to those in the active control. The outcome measure used to quantify this endpoint is the PROMIS® PF short-form, a validated self-report of physical function. The	The PROMIS® PF short- form scale is a widely validated instrument with excellent content validity, construct validity, and reliability in patients with spinal disorders and other conditions marked by

OBJECTIVES	ENDPOINTS	JUSTIFICATION FOR ENDPOINTS
	outcome measure is administered on a weekly basis via a smartphone survey to capture longitudinal change and variation among participants.	diminished mobility. The outcome measure allows us to place patients on a continuum of physical function with respect to various physical actions.
Secondary		
The secondary objective of this study is to investigate the efficacy of a multi-modal digital pain reduction kit in reducing pain interference over time, work productivity, opioid use, and satisfaction with care.	The secondary endpoints of are clinically significant changes in pain interference, work productivity, use of opioids, and satisfaction with healthcare among those in the intervention arm compared to participants in the active control. Outcome measures include pain interference (PROMIS® Pain Interference, measured weekly via smartphone surveys), work absenteeism and presenteeism (WPAI:LB, measured at baseline and exit surveys), number of 90 Morphine Milligram Equivalent opioid prescriptions (obtained via cumulative EHR records), and satisfaction with healthcare (CG- CAHPS, measured once at the conclusion of the study).	
Tertiary/Exploratory		
N/A	N/A	N/A

4 STUDY DESIGN

4.1 OVERALL DESIGN

This RCT will enroll 174 patients with pain due to musculoskeletal injuries to test the efficacy of a multi- model digital pain reduction kit on short term pain management as an adjunct to traditional medical therapy. We will attempt to enroll a minimum of 90 patients reporting lower back pain specifically, as patients without lower back pain are less likely to use the TENS unit. Prior to adding the TENS unit to the control arm, we recruited 24 control patients. However, we will not discard their data since we intend on performing a supplementary sensitivity analysis. In addition to these 24 controls, we will randomize 75 patients to receive the study intervention (multi-modal digital pain-reduction kit with optional remote coaching support), and the other 75 patients will receive an active control. We will allocate patients using a random number generator to ensure that there is an equal distribution of participants in the control vs. experimental group. The primary outcome will be changes in self-reported physical function measured by the Patient Reported Outcome Measurement Information System (PROMIS®) Physical Function Scale. Secondary outcomes will include PROMIS® Pain Interference Scale, PROMIS® Global Health Scale, work productivity and activity impairment questionnaire (WPAI) (for patients with lower back pain specifically), patient satisfaction measured by the Pain Treatment Satisfaction Scale and SF Patient-Satisfaction Questionnaire), and use of opioids (measure in morphine milligram equivalents).

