5.5 STRATEGIES FOR RECRUITMENT AND RETENTION

Male and female participants above the age of 18 will be screened to reach target enrollment 174 patients over a period of 16 months. Participants presenting with pain due to a musculoskeletal injury will be screened and enrolled at four sites (Cedars Sinai Orthopedic Clinic, Medical Delivery Network, Cedars Sinai Pain Management Clinic, Medical College of Wisconsin). Patients will be identified and approached by their providers. The treating physicians will contact their patients during their clinic visits and assess the patient's willingness to be contacted about the research and the treating physician will document the patient's willingness to be contacted on the *CSMS Research Interest* letter. The Research Letter will be tailored to each clinical practice of the treating provider. Additionally, participating providers will distribute recruitment pamphlets to patients in clinic and/or through mail. Should the patient be interested in being contacted about the study, the study team will then approach the patient for

participation in the research either in person or over-the-phone. The patient will have the option to complete their consent forms on paper or electronically using the 21 CFR 11-compliant online platform, DocuSign. Every subject will be informed of the approximate time to complete the consent process. Consenting will be done with a research staff member either in-person or remotely via DocuSign to ensure the identity of the person signing the informed consent form is indeed the subject participating in the research study. A copy of the informed consent documents will be given to the participants for their records via their email or a physical hard copy. Participants who consent remotely will receive their study equipment through a secure FedEx package requiring a signature. Retention to the 60-day study for the intervention group will be managed using weekly reminders to complete survey protocols, as well as optional opt-in monitoring of compliance and health data via remote clinical and technical support staff. Participants will not receive monetary compensation for participating in this study.

Participants experiencing lower back pain will be oversampled to a minimum of 45 per arm in order to obtain sufficient sample size for testing the success of the TENS unit.

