6.2 MEASURES TO MINIMIZE BIAS: RANDOMIZATION AND BLINDING

Per the new protocol, participants will be randomized intervention or control until intervention and control groups each have 75 enrollees. In addition to these 150 participants, the group of 24 controls that were originally recruited without the TENS unit will remain accounted for in the supplementary analysis. There will be no blinding, as participants in the control group will be aware that they are missing components of the intervention as detailed in the consent form.

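### A minimum of 90 low-back-pain patients gives at least 45 per arm only if they split exactly evenly, and the plan describes no strata, blocks or margin to achieve this

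*Combined protocol and SAP*

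**What the plan says.** Section 4.1 (Overall Design) gives the allocation method: "We will allocate patients using a random number generator to ensure that there is an equal distribution of participants" between control and intervention. It also sets a target for one subgroup: "We will attempt to enroll a minimum of 90 patients reporting lower back pain specifically". Its reason is that other patients are less likely to use the TENS device.

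Section 5.5 (Strategies for Recruitment and Retention) restates the target by arm: "Participants experiencing lower back pain will be oversampled to a minimum of 45 per arm". The purpose given there is to have enough patients to assess TENS. It also says that participants "will be screened and enrolled at four sites".

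Section 6.2 (Randomization and Blinding) adds a cap: "participants will be randomized intervention or control until intervention and control groups each have 75 enrollees". It also states that there is no blinding. Outside these 150 patients are controls enrolled under the previous design: "Prior to adding the TENS unit to the control arm, we recruited 24 control patients".

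The plan describes no strata, block size, preparation of the sequence or concealment. It does not say how the low-back-pain minimum in each arm is to be enforced. The potential covariates in Section 9.1 include neither low-back-pain status nor site.

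**The concern.** The target in Section 5.5 is exactly half of the target in Section 4.1, so the plan leaves no margin for chance. An unstratified generator seldom splits 90 patients exactly 45 to 45. If low-back-pain recruitment stops at its minimum total, the minimum per arm will probably be missed.

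The plan itself ties this subgroup to use of the TENS device, and TENS is now in both arms. A chance imbalance in low-back-pain status would therefore tend to shift TENS use between the arms in the primary comparison. As written, the design does not prevent that imbalance, and the listed covariates do not adjust for it.

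**Working it through.** **Inputs.** At least 90 low-back-pain patients in total (4.1); at least 45 per arm (5.5); 75 per arm, 150 in all (4.1, 6.2); effect size 0.6 SD, 80% power and a level of 0.05 (9.2; taken as two-sided, since the plan does not say).

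**The plan's own figures.** 2 x 45 = 90 and 75 + 75 + 24 = 174 both reproduce.

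**Two models for L low-back-pain patients.** Let X be the number in one arm. The minimum is met when 45 <= X <= L - 45.
- Simple 1:1 allocation without a cap: X ~ Binomial(L, 0.5).
- Arms held to 75/75, with low-back-pain patients falling at random among the 150: X ~ Hypergeometric(150, 75, L).

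At L = 90 the only admissible value is X = 45:
- Simple: C(90,45) / 2^90 = 0.084.
- Capped: C(75,45)^2 / C(150,90) = 0.132.

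| At L = 90 | Simple | Capped at 75/75 |
|---|---|---|
| At least 45 in both arms | 8.4% | 13.2% |
| Median of smaller arm | 42 | 43 |
| 5th percentile of smaller arm | 36 | 39 |
| Arms differ by 10 or more | 34% | 13% |

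| Low-back-pain total | Simple: both arms at least 45 | Capped: both arms at least 45 |
|---|---|---|
| 96 | 52% | 77% |
| 99 | 69% | 92% |
| 100 | 73% | 94% |
| 106 | 90% | 99.8% |
| 110 | 96% | >99.9% |

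The chance first reaches 90% at 106 patients (simple) or 99 (capped). Recruiting under simple allocation until both arms reach 45 takes about 98 low-back-pain patients on average (95th percentile 110), which fits within 150.

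**What the cap does.** Without it, 150 simple allocations give exactly 75/75 with probability C(150,75) / 2^150 = 6.5%. With it, 75/75 is certain if enrolment completes. Once one arm is full, though, every remaining patient must go to the other. By simulation this forces about the last 10 allocations on average (5th to 95th percentile about 1 to 23).

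**What stratified blocks would do.** Block sizes of 4 and 6 are assumed.
- *Low-back-pain status only, 90 patients.* Blocks of 6 give 15 full blocks, so always 45/45. Blocks of 4 give 22 full blocks and half of another. That half block splits evenly with probability 4/6, so the result is 45/45 about two times in three and otherwise 44/46.
- *Low-back-pain status by site, three or four equal sites, 90 patients.* By simulation, 45/45 occurs in about 36% to 49% of runs, and the smaller arm never fell below 42. At 94 patients both arms reach 45 in at least 98% of runs, and at 96 in all runs.

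**Power within the low-back-pain subgroup.** For a two-sample t-test with no dropout, the noncentrality is 0.6 x sqrt(n1 n2 / (n1 + n2)). For 45/45 it is 0.6 x sqrt(22.5) = 2.85, giving 80.4% power. For 36/54 it is 0.6 x sqrt(21.6) = 2.79, giving 78.8%. A 40/50 split gives 79.9%.

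**The case against.** The strongest reply is that 90 is a floor, not a ceiling. Section 4.1 calls it a minimum, and Section 5.5 states the target per arm and says these patients will be oversampled. If 100 are enrolled within the 75/75 cap, both arms reach 45 with probability 94%. This stands: the documents do not show that the minimum must be missed. They show only that the stated total does not deliver it, and that no larger total or continuation rule is written down.

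A reader might also infer that a random number generator cannot give the equal distribution that Section 4.1 promises. Section 6.2 rules that out for the overall totals, because the cap makes them equal. What remains is the predictable run of allocations at the end, in an open-label trial with no concealment described.

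Nor do the documents support calling low back pain the main prognostic factor. Section 4.1 links it to device use, not to the course of physical function. Chance imbalance under randomisation does not bias the comparison in expectation, and the power cost above is under two percentage points.

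Finally, stratifying by site is reasonable practice, but no stated target depends on it. With low-back-pain status by site, an exact 45/45 from 90 is less likely than with low-back-pain strata alone.

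**Conclusion.** The point holds in limited form. The total of 90 and the minimum of 45 per arm fit together only under an exact split. At exactly 90, the minimum is missed about 87% of the time under the cap and about 92% under simple allocation. This is a gap in how a stated target is to be met, and an avoidable source of imbalance on a factor that the plan links to TENS use. It does not invalidate the trial or materially reduce its power.

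The figures assume 1:1 allocation, no undocumented blocking, and low-back-pain patients arriving at random among the 150. The documents do not say whether any of the 24 controls without TENS count towards the 90 or the 45, or whether intervention patients randomised alongside them count towards the 75. If, as an assumption, 24 intervention patients already count, allocating 1:1 to the remaining 51 intervention and 75 control places would force about 24 allocations on average, nearly all to control.

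**What to change.** 1. For patients still to be randomised, specify a concealed permuted-block sequence stratified by low-back-pain status, preferably with varied block sizes. State how the cap of 75 per arm works with it.
2. Add low-back-pain status as a fixed covariate in the primary mixed model (Sections 9.1 and 9.4.2).
3. Either set the low-back-pain target at about 94 to 96, or state that low-back-pain recruitment continues within the 150 until each arm has 45. The second is safer if an imbalance already exists, because blocks applied from now on do not undo it.
4. State whether patients enrolled before TENS was added to the control arm count towards these targets.
5. Institution can be added as a model covariate. As a stratum it is optional.

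Low-back-pain status can be recorded at enrolment, so the change needs one field in the randomisation list and one or two model terms. The cost is an IRB-approved amendment partway through the trial and a clear cut-over for patients already allocated. The gain is better balance and a minimum that is likely to be met. Little change in power should be expected.

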4.2 SCIENTIFIC RATIONALE FOR STUDY DESIGN

The active control group in the randomized control trial minimizes biases related to reactivity administering standard care of care in addition to a passive measurement component. Therefore, the control group may show some effect and limit the effect size of the intervention, given that TENS units have been shown to reduce pain, at least in the short term.

4.3 JUSTIFICATION FOR DOSE

The TENS unit and VR are to be used as needed during patient flares of pain. The three daily doses are a recommendation and patients may deviate as necessary contingent on their pain levels.

4.4 END OF STUDY DEFINITION

A participant is considered to have completed the study if he or she has completed all components of the study including the last visit shown in the Schedule of Activities (SoA), Section 1.3.

The end of the study is defined as completion of the last visit shown in the SoA in the trial globally.

5 STUDY POPULATION

5.1 INCLUSION CRITERIA

In order to be eligible to participate in this study, an individual must meet all of the following criteria:

- 1. Provision of signed and dated informed consent form
- 2. Stated willingness to comply with all study procedures and availability for the duration of the study
- 3. Male or female, aged 18 or older
- 4. Seeking care for a musculoskeletal injury
- 5. Experiencing pain greater than 3 out of 10 on a visual analog scale
- 6. English speaking
- 7. Owns a compatible Android or iOS smartphone device (excluding tablets)

5.2 EXCLUSION CRITERIA

An individual who meets any of the following criteria will be excluded from participation in this study:

- 1. Unable to understand the goals of the study due to cognitive difficulty
- 2. Pregnant (contraindication for TENS unit)
- 3. Use of a cardiac pacemaker, implanted defibrillator, or other implanted metallic or electronic device or high frequency surgical equipment. (contraindication for TENS units)
- 4. Current diagnosis of epilepsy, dementia, or other neurological disease that may prevent use of VR hardware or software
- 5. Hypersensitivity to flashing light or motion
- 6. Injury to the eyes, face, neck, or arms that prevents comfortable use of VR hardware or software, or safe use of other study hardware (e.g., open sores, wounds, or skin rash on face)

5.3 LIFESTYLE CONSIDERATIONS

N/A

5.4 SCREEN FAILURES

Screen failures are defined as participants who consent to participate in the clinical trial but are not subsequently randomly assigned to the study intervention or entered in the study. A minimal set of screen failure information is required to ensure transparent reporting of screen failure participants, to meet the Consolidated Standards of Reporting Trials (CONSORT) publishing requirements and to respond to queries from regulatory authorities. Minimal information includes demography, screen failure details, eligibility criteria, and any serious adverse event (SAE).

Individuals who do not meet the criteria for participation in this trial (screen failure) because of a will not be rescreened.

5.5 STRATEGIES FOR RECRUITMENT AND RETENTION

Male and female participants above the age of 18 will be screened to reach target enrollment 174 patients over a period of 16 months. Participants presenting with pain due to a musculoskeletal injury will be screened and enrolled at four sites (Cedars Sinai Orthopedic Clinic, Medical Delivery Network, Cedars Sinai Pain Management Clinic, Medical College of Wisconsin). Patients will be identified and approached by their providers. The treating physicians will contact their patients during their clinic visits and assess the patient's willingness to be contacted about the research and the treating physician will document the patient's willingness to be contacted on the *CSMS Research Interest* letter. The Research Letter will be tailored to each clinical practice of the treating provider. Additionally, participating providers will distribute recruitment pamphlets to patients in clinic and/or through mail. Should the patient be interested in being contacted about the study, the study team will then approach the patient for

participation in the research either in person or over-the-phone. The patient will have the option to complete their consent forms on paper or electronically using the 21 CFR 11-compliant online platform, DocuSign. Every subject will be informed of the approximate time to complete the consent process. Consenting will be done with a research staff member either in-person or remotely via DocuSign to ensure the identity of the person signing the informed consent form is indeed the subject participating in the research study. A copy of the informed consent documents will be given to the participants for their records via their email or a physical hard copy. Participants who consent remotely will receive their study equipment through a secure FedEx package requiring a signature. Retention to the 60-day study for the intervention group will be managed using weekly reminders to complete survey protocols, as well as optional opt-in monitoring of compliance and health data via remote clinical and technical support staff. Participants will not receive monetary compensation for participating in this study.

Participants experiencing lower back pain will be oversampled to a minimum of 45 per arm in order to obtain sufficient sample size for testing the success of the TENS unit.

6 STUDY INTERVENTION

6.1 STUDY INTERVENTION(S) ADMINISTRATION

6.1.1 STUDY INTERVENTION DESCRIPTION

Study Intervention: Digital Pain Reduction Kit

The study intervention will include evidence-based digital devices that offer non- pharmacological solutions to managing pain. Patients in the intervention group will receive access to two devices: (1) Oculus Go headset or PICO G2 headset with preloaded therapeutic visualization software developed by appliedVR; (2) Aleve® Direct Therapy TENS Device. Study staff will monitor patient progress remotely and provide guided support and coaching. The sections, below, describe the components of the intervention.

Smartphone, VR Headset, and Software

To care for the whole patient, clinicians must consider not only the physical impact of illness, but also the psychosocial impact. However, the dynamic nature of clinical medicine, coupled with limited time to spend with individual patients, pose challenges to offering holistic care for patients with pain.

Treatment of pain is often focused on pharmacological management which can yield inconsistent and sub-optimal pain control.[2] However, extensive data reveal that adjunctive non-pharmacological techniques, such as cognitive behavioral therapy and relaxation techniques, can modify cognitions and behaviors that influence the perception of pain.[3] VR technology provides an immersive, multisensory, and three-dimensional (3D) environment that enables users to have modified experiences of reality by creating a sense of "presence".[4 5] To date, VR has been used in numerous clinical settings to help treat anxiety disorders, control pain, support physical rehabilitation, and distract patients during wound care.[4-12] For example, VR coupled with medication is effective in decreasing pain during bandage changes for severe burns.[6 10 13 14] Similarly, VR reduces pain and provides positive distraction during routine procedures, such as intravenous line placements[9] and dental procedures.[7 15] Other studies reveal that VR helps manage chronic pain conditions such as complex regional pain syndrome[16] and chronic neck pain.[17] Our own research shows that VR can reduce pain by an average of 24% among hospitalized patients with a wide

range of somatic and visceral pain. By stimulating the visual, auditory, and proprioception senses, VR acts as a distraction to limit the user's processing of nociceptive stimuli.[5]

However, despite the evidence and increasing media attention surrounding VR, there have been no controlled trials using VR at scale to manage outpatient musculoskeletal pain, particularly low back pain (the most common reason for worker compensation claims and lost productivity).

This RCT will use a Oculus Go or PICO G2 all in one head mounted display that delivers VR images and sound. We selected the Oculus Go and PICO G2 because they are commercially available, widely used, inexpensive, have minimal visual latency, and are much easier for patients to use than devices used in our previous research. [18] Higher end tethered headsets, such as the Oculus Rift, are currently more expensive and onerous to use at scale in an inpatient setting.

Users will wear the VR goggles. Detailed instructions will familiarize patients with hardware; and telephonic and email technical support from study staff will be available to advise patients having trouble using the equipment. Patients unable to use the device at home will be offered an in-person visit with study staff to troubleshoot and train.

We will use the appliedVR app to offer >30 therapeutic VR experiences through the headsets. Our team has worked with appliedVR to curate experiences that are acceptable to a wide range of patients. The app includes a menu of visualizations, each mapped to a therapeutic benefit (e.g. pain reduction, anxiety reduction, mindful meditation).

The app includes "Pain RelieVR", a 15-minute VR experience specifically designed to treat pain in patients with limited mobility. Pain RelieVR is an immersive, 360-degree game experience that takes place in a fantasy world where the user attempts to shoot balls at a wide range of moving objects by maneuvering their head towards the targets. This engaging, medium-intensity activity is free of interruption, offering the user a distracting experience designed to reduce the perception of pain. Pain RelieVR is a non-violent and non-competitive game that incorporates motivational music and features positively reinforcing sounds, animation and direct messages to patients. Forward- facing action allows patients with limited mobility to engage without having to turn backwards or contort into potentially uncomfortable positions.

The app also includes "Anxiety RelieVR," an interactive, meditative landscape along a peaceful shoreline . In contrast to Pain RelieVR, which acts through distraction therapy, Anxiety RelieVR employs mindful meditation to help manage the affective component of pain. These cornerstone experiences are supported by a wide range of additional therapeutic journeys, including an Iceland flyover in a helicopter, an undersea experience, and a variety of nature-related experiences, among many others.

Patients can pick and choose which visualizations to watch based on their own preferences. In clinical testing, we asked patents to use the headset at least thrice daily, for 10 minutes per treatment period, and to also use as needed for breakthrough pain between treatments. The appliedVR software allows our team to monitor adherence with the therapy, including the visualizations selected by the user, the amount of exposure time, and the time of day the visualization was viewed.

TENS Device

We will supplement therapeutic VR with TENS, another evidence-based, non-invasive, non-pharmacological pain reduction technique. TENS employs an electric current to stimulate nerves in a manner thought to release intrinsic endorphins and to block transmission of nociceptive signals. Data measuring brain function with evoked cortical potentials and functional magnetic resonance imaging (fMRI) suggests that TENS may suppress pain signals centrally, in addition to its direct peripheral benefits on the sensory nerves. Although clinical evidence is inconsistent among studies, types of pain (chronic vs. acute), and location of pain, TENS units have been FDA cleared as a class II device for many years, and consumer satisfaction with these devices is consistently high.

Clinical data reveal benefits of TENS for lower back pain. In a recent meta-analysis of RCTs, cohort studies, and randomized crossover studies for TENS in lower back pain, Jauregui and colleagues determined the technique significantly reduces pain intensity, particularly for short term treatment (<5 weeks).[19] The authors concluded that TENS may lead to less pain medication usage and should be incorporated into the treatment armamentarium for low back pain.

For this study, we will use an over-the-counter, consumer-facing product called the Aleve Direct Relief TENS Device. This device is designed for use over the lower back for management of pain of lumbosacral origin. Treatment periods last 30 minutes and include three stages. In stage I, the device emits 5 minutes of high frequency stimulation (>50 Hz) to initiate anti-nociceptive effects through diminished processing of pain signals. In stage II, the device emits 20 minutes of low frequency stimulation (<20 Hz) to release endorphins as a second mechanism of pain reduction. The treatment period ends with stage III, in which another 5 minutes of high frequency stimulation is deployed with the aim of maintaining the initial pain relief established by phases I and II. Patients receive a handheld remote control to adjust the intensity of the electrical stimulation based on personal preference and tolerance. The device is used as needed for breakthrough pain, or as baseline prophylactic treatment.

Clinical and Technical Support

Patients in the intervention arm will not only receive the digital pain reduction kit, but also will receive remote technical and clinical support from the research team. The idea is that issuing devices is usually insufficient to achieve behavior change; supporting those device with high-touch yet scalable care is a vital component.

Rationale for "Digitalist" Model of Remote Clinical Monitoring

Integrating digital technologies into a harmonized health delivery model may improve process and outcomes of care. If used effectively, digital health monitoring may tailor care to individual patients, extend clinicians' reach outside of the hospital and clinic, improve timeliness and specificity of care, deliver proactive (not reactive) care, and better engage patients in their health.[20]

Still, there are important questions we need to answer: Who will be checking all the data? How can doctors, who are busy in the clinical trenches, be responsible for monitoring and acting upon the data streaming off wearable sensors, apps, and patient-provider portals? Who has time for this? The reality is that no doctor has enough bandwidth to check mobile health (mHealth) data on a regular basis. Clinicians are too busy for this work.[20]

One answer for moving digital health forward is to develop a new type of specialist called the "Digitalist."[20] The Digitalist does not yet exist at scale, just as "The Hospitalist" did not exist prior to 1996, when Robert Wachter and Lee Goldman coined the term to describe a much-needed clinician to fill an unmet need for inpatient care.[21] Now we have an unmet need for a new clinician (though not necessarily a physician), trained in digital health, who will monitor, interpret, and act upon remote patient data – in this instance among patients recovering from a low back injury. In this study, a health coach, acting similar to a Digitalist, will remotely track data from biosensors, portals, and apps, then combine the data to provide guidance with adhering to the intervention.

Patients transmit actively and passively collected data through apps and portals. The Digitalist monitors the data, and, if needed, contacts the patient via EHR portal, telephone, or videoconferencing. If appropriate, the Health Coach communicates directly with clinicians, informs them of updates, and coordinates the optimal timing of in-person visits. The clinician may also access digital health reports, review the results with the patient, and make further decisions based on the data coupled with the traditional history and physical examination.

This model has potential to expand care beyond the traditional clinic visit, uses visits more effectively, reduces avoidable admissions, and improves outcomes of care.

Implementation of Health Coach Model in Intervention Arm

In the current study, we will simulate aspects of the Health Coach model by allowing patients in the intervention arm to remotely share their secure mHealth data with selected members of the research team. VR usage data will also be transmitted remotely through the appliedVR app, allowing our team to monitor adherence with the VR intervention. We will assign two staff to monitor patients in the control arm: (1) technical support staff member, and (2) Health Coach. Patients will receive a telephone number and email to contact support staff as needed. The technical support staff will also reach out if there is low adherence with the devices, prolonged missing wearable data, or low battery power detected on the remote monitoring dashboard. The Health Coach will reach out if there is evidence of worsening physiologic or activity parameters (e.g. walking less, sleeping less, heart rate increasing) using their clinical judgment. Patients will be informed to contact 911 and/or call their physician directly if they experience any urgent, semi-urgent, or concerning signs or symptoms. The Health Coach will check mHealth data logs twice weekly on weekdays, and contact the patient by phone according to the patient's stated preferences. Patients who do not want Health Coach remote monitoring will not receive this component of the intervention but will still be included in the intention-to-treat population.

